6.3.2 Secondary Efficacy Endpoints

- Pharmacokinetic parameters of BGB-290 and TMZ, including but not limited to C_{trough}
Refer to Section 6.3.6 for more detail.
- Disease Control Rate (DCR) by investigator

DCR is defined as the proportion of subjects with BOR of CR, PR, or stable disease (SD). Similar to ORR, two-sided binomial exact 90% confidence intervals will be calculated for DCR in each cohort. The table for DCR will be summarized in both SAF and Efficacy Evaluable Analysis Set. Patients without evaluable postbaseline tumor assessment will be considered as non-responders in the safety analysis set.

- Duration of Response (DOR) by investigator

DOR is defined as the time (month) from the date of the earliest documented CR or PR (that is subsequently confirmed) to disease progression or death due to any cause, whichever occurs earlier. The tables for confirmed and nonconfirmed DOR will be summarized in efficacy evaluable set and only responders will be included in the DOR calculation.

Kaplan-Meier method will be used to estimate DOR, and corresponding quartiles (including the median) in the responders. A two-sided 90% CIs of median will be calculated for each cohorts using generalized Brookmeyer and Crowley method (Brookmeyer & Crowley, 1982).

Censoring rule for DOR will follow PFS censoring rule mentioned in FDA Guidance for Industry Clinical Trial Endpoints for the Approval of Cancer Drugs and Biologics (2018). The censoring rules are described in Appendix 10.2.

- PFS and PFS-6m by investigator

PFS is defined as the time (months) from the date of the first dose of combination treatment to disease progression or death due to any cause, whichever occurs first. The PFS-6m is defined as the percentages of subjects who remain alive and progression-free at 6 months. PFS censoring rules are described in Appendix 10.2. If a patient meets the criteria for more than 1 censoring rule, PFS will be censored at the earliest censoring date. The tables for PFS and PFS-6m will be summarized in Efficacy Evaluable Analysis Set.

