Kaplan-Meier method will be used to estimate PFS and PFS-6m, and corresponding quartiles (including the median) in the responders. A two-sided 90% CIs of median, Q1 and Q3 will be calculated for each cohorts using generalized Brookmeyer and Crowley method (Brookmeyer & Crowley, 1982). Event free rate at the specified time point (e.g., 3, 6, 9 or 12 months) will be estimated using the Kaplan-Meier method along with the corresponding 90% CI constructed using Greenwood's formula.

- **OS and OS-6m**

OS is defined as the time (months) from the date of the first dose of combination treatment to death due to any cause. Deaths that occur on or before the data cutoff date will be considered as an event. Data from patients who are alive on or before the data cutoff date will be censored at the last known alive date. The OS-6m is defined as the percentages of subjects in the analysis population who remain alive and progression-free at 6 months. The tables for OS and OS-6m will be summarized in SAF.

Kaplan-Meier method will be used to estimate OS and OS-6m, and corresponding quartiles (including the median) in the responders. A two-sided 90% CIs of median, Q1 and Q3 will be calculated for each cohorts using generalized Brookmeyer and Crowley method (Brookmeyer & Crowley, 1982). Event free rate at the specified time point (e.g., 3, 6, 9 or 12 months) will be estimated using the Kaplan-Meier method along with the corresponding 90% CI constructed using Greenwood's formula.

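### SAP 6.3.2 restricts the Kaplan-Meier estimates of PFS and OS to responders, against its own analysis sets, and keeps an OS-6m definition that conflicts with the protocol and with Section 8

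*SAP*

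**What the plan says.** All of the wording at issue is in SAP 6.3.2.

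- **Duration of response.** "Kaplan-Meier method will be used to estimate DOR, and corresponding quartiles (including the median) in the responders". The paragraph also says "only responders will be included in the DOR calculation". The restriction belongs here, because the endpoint exists only for responders.
- **PFS.** The population is given as "The tables for PFS and PFS-6m will be summarized in Efficacy Evaluable Analysis Set". The estimation sentence that follows reads "Kaplan-Meier method will be used to estimate PFS and PFS-6m, and corresponding quartiles (including the median) in the responders".
- **OS.** The population is given as "The tables for OS and OS-6m will be summarized in SAF". The estimation sentence reads "Kaplan-Meier method will be used to estimate OS and OS-6m, and corresponding quartiles (including the median) in the responders".
- **OS-6m.** "The OS-6m is defined as the percentages of subjects in the analysis population who remain alive and progression-free at 6 months".
- **Landmark rates, for both PFS and OS.** "Event free rate at the specified time point (e.g., 3, 6, 9 or 12 months) will be estimated using the Kaplan-Meier method".

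Elsewhere, SAP 6.1 names the Safety Analysis Set for overall survival. SAP Section 8 lists the move of OS to that set as a change from the protocol, and says that PFS-6m and OS-6m will not be analysed. Protocol 11.2.5 limits only DOR to responders, presents median PFS, DOR and OS by cohort, and defines OS-6m as being alive at 6 months.

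**The concern.** One section gives two answers to the question of who is in the PFS and OS curves. Responders are a subset of both named sets, so the two instructions cannot both be followed.

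The choice affects the results. PFS and OS run from the first dose of combination treatment, but responder status is known only at a later scan, and a patient must still be alive and progression-free to reach it. Restricting the analysis to responders guarantees them event-free time at the start of the curve and removes the patients who failed early. The estimates then look better than those of the treated cohort, even if response has no bearing on later risk.

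The OS-6m wording raises a second problem. Its definition counts progression as a failure, while the 6-month OS event-free rate in the same paragraph counts only death. One paragraph would therefore produce two different figures for 6-month survival, and Section 8 says that PFS-6m and OS-6m are not produced at all.

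**Working it through.** **1. Which population the documents support**

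| Source | PFS | OS |
|---|---|---|
| SAP 6.1 | not named | Safety Analysis Set |
| SAP 6.3.2, table sentence | Efficacy Evaluable set | Safety Analysis Set |
| SAP 6.3.2, Kaplan-Meier sentence | responders | responders |
| SAP 8 | no responder restriction listed | Safety Analysis Set |
| Protocol 11.2.5 | by cohort, no restriction | by cohort, no restriction |

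The Kaplan-Meier sentences for PFS and OS differ from the DOR sentence only in the endpoint name. Carry-over from the DOR paragraph is the likely cause, but that is an inference. The conflict itself is plain from the text. SAP 6.3.1 reports both confirmed and unconfirmed responses, and the PFS and OS sentences do not say which kind of responder they mean.

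**2. Patients left under the literal reading**

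SAP Section 5 plans 20 to 25 patients per cohort and an ORR of about 40%. Its Table 1 reproduces with exact 90% intervals (8/20: 21.7% to 60.6%; 10/25: 23.6% to 58.3%), so the planning case is sound.

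- Responders at 40%: 0.40 × 20 = 8 and 0.40 × 25 = 10.
- Responders at an assumed 20%: 4 and 5.
- The 90% half-width for a 6-month rate near 50%, without censoring, is 1.645 × √(0.25/n). For n = 25, 20, 10 and 8 this gives 0.1645, 0.184, 0.260 and 0.291.

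The half-width therefore goes from about 16–18 to 26–29 percentage points.

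**3. Size of the upward shift**

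The medians below are assumptions, because the documents give none. Times are exponential with median m, and response is unrelated to later hazard. One month is 30.4375 days (SAP 6.2.2). The first scan is at week 8 (Protocol 7.7), so t = 56/30.4375 = 1.84 months. Confirmation needs at least 4 more weeks, so its earliest time is week 12, t = 84/30.4375 = 2.76 months.

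Given no event by t, the median from first dose is m + t, and the 6-month rate is 2^(−(6 − t)/m).

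| Endpoint, assumed m (months) | Median: all → week 8 → week 12 | 6-month rate: all → week 8 → week 12 |
|---|---|---|
| PFS, 4 | 4.00 → 5.84 → 6.76 | 0.354 → 0.486 → 0.570 |
| PFS, 3 | 3.00 → 4.84 → 5.76 | – |
| PFS, 6 | 6.00 → 7.84 → 8.76 | – |
| OS, 9 | 9.00 → 10.84 | 0.630 → 0.726 |
| OS, 12 | 12.00 → 13.84 | 0.707 → 0.786 |

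Simulation of 2,000,000 times agrees (PFS, m = 4: 5.85 and 0.487 at week 8; 6.76 and 0.571 at week 12).

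A second model lets responders differ from non-responders. Response occurs at week 8, and ORR is 20% or 40%. Median PFS after response, paired with the median in non-responders, is 8 and 2, 8 and 4, or 6 and 6 months. Median PFS is then 2.7 to 6.8 months in all patients and 7.8 to 9.9 in responders. The 6-month rates are 24% to 55% and 62% to 70%.

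**4. The two meanings of OS-6m**

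The 6-month rate is 2^(−6/m), using the PFS median for alive and progression-free and the OS median for alive.

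| Assumed median PFS / OS (months) | SAP wording | Protocol wording |
|---|---|---|
| 3 / 9 | 25% | 63% |
| 4 / 9 | 35% | 63% |
| 4 / 10 | 35% | 66% |
| 6 / 12 | 50% | 71% |

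**The case against.** The strongest reply is that the documents settle the population themselves. OS is assigned to the Safety Analysis Set in three places and PFS to the Efficacy Evaluable set in one. The confidence-interval sentence directly after each disputed sentence speaks of each cohort, and Section 8 lists no responder restriction. A careful programmer would probably use the named sets. This supports calling the phrase a slip. It does not remove the conflict, and a plan for an open-label study should not leave the choice to be made after data are seen.

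The responder phrase could also be read as attaching only to the quartiles and median. That spares the curves and the landmark rates, but the median is the headline figure and would still be inflated.

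On OS-6m, Section 8 says the analysis is not done, so the wrong definition may produce no output, and the landmark months are offered only as examples. That limits the harm. But Section 8 states the SAP's current departures from the protocol, not superseded text, so its clash with 6.3.2 is live.

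The first PFS censoring rule (SAP 10.2, Table 3) covers patients with no post-baseline assessment, none of whom can be responders. It is only partial evidence of intent, because many such patients also fall outside the Efficacy Evaluable set. Those who stop for clinical progression before a scan fall inside it.

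Finally, the sizes depend on assumed medians and on the model, as the two illustrations show. The direction does not.

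**Conclusion.** The concern holds and should be fixed. SAP 6.3.2 contradicts itself on the Kaplan-Meier population for both PFS and OS. It gives OS-6m the definition of PFS-6m, against the protocol, and it specifies 6-month endpoints that Section 8 removes.

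If the responder sentences were followed, each cohort's curves would rest on 8 to 10 patients at the planning ORR, and the estimates would be biased upward. Under exponential times with a 4-month median PFS, the week 8 condition alone adds 1.84 months to the median and 13 points to the 6-month rate (48.6% − 35.4% = 13.2). These sizes apply only to the literal reading and the assumed medians.

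The endpoints are secondary and no hypothesis test is planned. The effect is on reported estimates, not on error rates, sample size, the primary endpoints or dose decisions.

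**What to change.** In SAP 6.3.2:

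1. Delete the words *in the responders* from the Kaplan-Meier sentences for PFS and OS, and keep them for DOR. PFS is then estimated in the Efficacy Evaluable set and OS in the Safety Analysis Set.
2. Either define OS-6m as the Kaplan-Meier probability of being alive at 6 months, as in Protocol 11.2.5, or delete it.
3. Make 6.3.2 and Section 8 agree on whether 6-month rates are reported. If they are dropped, remove PFS-6m, OS-6m and the 6-month example among the event-free rates. If they are kept, amend Section 8.

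The cost is an edit to the SAP text. It needs no new data and adds no programming work.

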6.3.3 Subgroup Analyses

ORR and DCR will be summarized for patients with SCLC in the expansion stage in subgroups of

- chemosensitivity
- number of prior regimens for advanced or metastatic disease (1, \geq 2)

6.3.4 CA-125 Assessment

For subjects with ovarian cancer, the CA-125 assessment result including elevated/normal and change from baseline (%) will be provided for each patient in a listing in SAF.

6.3.5 PSA Assessment

For subjects with prostate cancer, PSA will be evaluated. The PSA assessment result including change from baseline and nadir (%) will be provided for each patient in a listing in SAF.

6.3.6 Pharmacokinetic Endpoints

For subjects in BGB-290 PK intensive group who contributed full PK profiles up to 48 hours postdose of Cycle 1 Day 1, and up to 6 hours on Cycle 1 Day 15, the following PK parameters

will be derived: C_{max} , C_{2h} , T_{max} , $T_{1/2}$, AUC_{0-4h} , AUC_{0-inf} (Day 1), AUC_{last} , apparent clearance CL/F , and V_z/F (Day 1).

For the remaining subjects, PK parameters such as C_{min} will be summarized. Population PK analysis may be carried out to include plasma concentrations from this study in an existing model, and additional PK parameters such as apparent clearance of the drug from plasma (CL/F) and AUC may be derived if supported by data. Population PK analysis may be reported separately from the final CSR.

Trough and/or peak plasma concentrations of TMZ will be summarized and compared with appropriate historical control.

Exposure-response (efficacy or safety endpoints) analysis may be carried out if supported by data.

A summary of concentration for pamiparib (sparse and intensive sampling separately) and TMZ, and PK parameters for pamiparib, listings for concentration (pamiparib and TMZ separately) and parameters for pamiparib and figures of concentration vs time for intensive pamiparib PK sampling will be provided.

6.3.7 Exploratory Endpoints

Exploratory endpoints include blood and tumor biomarkers will be analyzed using the SAF. The correlation of predictive biomarkers with efficacy endpoints for study treatment will be explored.

6.4 SAFETY ANALYSES

All safety analyses will be performed by dose level in dose escalation phase and by cohort in dose expansion phase and by total (dose escalation and expansion phases combined). Safety will be assessed by monitoring and recording of all AEs graded by CTCAE v4.03. Laboratory values (hematology, serum chemistry, coagulation, and urinalysis), vital signs, physical exams and ECGs findings will also be used in determining the safety. Patients in SAF will be included for safety analyses.

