2. STUDY OBJECTIVES

2.1. Primary Objectives

- To determine the safety and tolerability of pamiparib when given orally in combination with temozolomide (TMZ; pulsed and continuous)
- To determine the maximum tolerated dose (MTD) or maximum administered dose (MAD) for pamiparib combined with TMZ (pulsed and continuous)
- To select the recommended Phase 2 dose and schedule of pamiparib in combination with TMZ
- To determine the antitumor activity of pamiparib in combination with TMZ

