11.2. Statistical Analysis

For the dose escalation phase, data will be summarized by dose level. For the dose expansion phase, data will be summarized by cohort.

Descriptive statistics will be mainly used in describing the anticancer activities and tolerability of the pamiparib and TMZ combination regimens. Confidence intervals will be constructed to describe the precision of the point estimates of interest (e.g. objective response rate and disease control rate).

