14. APPENDICES

APPENDIX 1. SCHEDULE OF ASSESSMENTS

Appendix 1 Table 1: Schedule of Assessments and Procedures Schedule for Dose Escalation and Dose Expansion Phases

Assessments	Pre-Screening (Dose Expansion only) ¹	Screening ²	Cycle 1 (28 days)				Cycles 2- 5 (28 days)		Cycle 6 and Subsequent Cycles in 1st year (Every 28 days)	Subsequent Cycles in the 2nd year and beyond (Every 28 days)	EOT ³	Safety Follow-up ⁴	Efficacy Follow-Up	Survival Follow-Up ⁵
			1	7	15	22	1	15						
Day of Phase	-84 to -29	-28 to -1	1	7	15	22	1	15	1	1	~7 days after last dose	~30 ± 7 days after last dose	Every 8 weeks	Every ~3 months
Allowed time window				-2 days ⁶	± 2 days	± 2 days	± 2 days ⁶	± 2 days	± 3 days	± 3 days			±7 days	
Pre-screening informed consent	X													
Informed consent		X												
Baseline demographics		X												
Medical and cancer history		X												
Complete Physical examination ⁷		X									X			
Limited physical examination ⁸			X	X	X	X	X	X	X	X				
Vital signs (including weight)		X	X	X	X	X	X	X	X	X	X			
Height		X												
ECOG performance status		X	X				X		X	X	X			
12-lead ECG ⁹		-14 to -1 X									X			
Triplicate ECGs ¹⁰			X		X									
Hematology ¹¹		-14 to -1 days X ¹²	X	X	X	X	X	X	X	X	X			
Clinical chemistry ¹¹		-14 to -1 X ¹²	X	X	X	X	X	X	X	X	X			

Assessments	Pre-Screening (Dose Expansion only) ¹	Screening ²	Cycle 1 (28 days)				Cycles 2- 5 (28 days)		Cycle 6 and Subsequent Cycles in 1st year (Every 28 days)	Subsequent Cycles in the 2nd year and beyond (Every 28 days)	EOT ³	Safety Follow-up ⁴	Efficacy Follow-Up	Survival Follow-Up ⁵
			1	7	15	22	1	15	1	1				
Day of Phase	-84 to -29	-28 to -1	1	7	15	22	1	15	1	1	~7 days after last dose	~30 ± 7 days after last dose	Every 8 weeks	Every ~3 months
Allowed time window				-2 days ⁶	± 2 days	± 2 days	± 2 days ⁶	± 2 days	± 3 days	± 3 days			±7 days	
Coagulation		-14 to -1 X ¹²												
Urinalysis ^{11,13}		-14 to -1 X ¹²												
Serum pregnancy test ¹⁴		-7 to -1 X												
Urine pregnancy test ¹⁵							X		X	X	X			
CT or MRI ¹⁶		X	EVERY 8 WEEKS ± 7 DAYS								X		X	
Tumor antigens ¹⁷		X	EVERY 8 WEEKS ± 7 DAYS								X		X	
HBV/HCV tests ¹⁸		X	As clinically indicated											
TMZ Dosing Dose escalation			Pulsed Dosing (Arm A): Once daily on Days 1 to 7 or Days 1-14 of each 28 day cycle Continuous Dosing (Arm B): Once daily continuously											
TMZ Dosing Dose Expansion			RP2D= 60 mg QD 60 mg QD Days 1-7 of each cycle											

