The dose expansion phase of the study will further evaluate the safety and anti-tumor activity of BGB-290 in combination with TMZ at the dose and schedule that will be chosen based on all data available including the dose escalation phase. This dose expansion phase will enroll patients in 6 different cohorts according to indication and/or homologous recombination deficiency (HRD) status as follows:

- Cohort 1: HRD positive (HRD+) ovarian cancer;
- Cohort 2: HRD+ triple-negative breast cancer (TNBC);
- Cohort 3: HRD+ metastatic castration-resistant prostate cancer (mCRPC);
- Cohort 4: Extensive Stage Small Cell Lung Cancer;
- Cohort 5: Gastric/Gastroesophageal Junction Cancer; and
- Cohort 6: patients who have HRD+ nonsquamous non-small cell lung cancer (NSCLC), squamous NSCLC, esophageal cancer, squamous head and neck cancer or soft-tissue sarcomas. Enrollment into these cohorts will occur simultaneously and independently.

For the interim clinical study report (CSR), only cohort 1 to 5 will be included. All cohorts will be included in the final CSR.

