6 STATISTICAL METHODS

No formal hypothesis testing will be conducted in this study. Data will be described mainly using descriptive statistics. Confidence intervals will be constructed to describe the precision of the point estimates of interest (e.g., objective response rate and disease control rate). Efficacy and safety analyses will be performed by dose escalation and dose expansion phases accordingly. Within dose escalation phase, data will be summarized by dose level within a dosing cohort or all combined. Within dose expansion phase, data will be summarized by cohort.

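### The SAP's safety tables have no column for all patients on the recommended dose and schedule; adding one would be a free improvement

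*SAP*

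**What the plan says.** SAP 6.4 fixes the grouping for all safety analyses: "by dose level in dose escalation phase and by cohort in dose expansion phase and by total (dose escalation and expansion phases combined". The general rules in SAP Section 6 are slightly wider for escalation, "Within dose escalation phase, data will be summarized by dose level within a dosing cohort or all combined", but not for expansion: "Within dose expansion phase, data will be summarized by cohort". Protocol 11.2 agrees: "For the dose expansion phase, data will be summarized by cohort". The list of changed analyses in SAP Section 8 adds no further grouping.

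The SAP study overview defines the expansion cohorts by disease, as "6 different cohorts according to indication and/or homologous recombination deficiency (HRD) status", and not by dose. In protocol Appendix 1 Table 1 the TMZ row for expansion gives a single regimen, "RP2D= 60 mg QD 60 mg QD Days 1-7 of each cycle", and the pamiparib row gives 60 mg twice daily. Escalation covers several flat TMZ doses (protocol 4.2.1), given for 7 days, 14 days or continuously (Appendix 1 Table 1).

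Adverse event incidence, nature and severity are a primary endpoint in both phases (SAP 4.1). One primary objective is "To select the recommended Phase 2 dose and schedule of pamiparib in combination with TMZ" (protocol 2.1), and the SAP study overview says that expansion evaluates safety further at the chosen dose and schedule.

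**The concern.** When the cohorts share one regimen, the natural denominator for a primary safety endpoint is everyone who started that regimen. The plan offers either one tumour group of 20-25 patients at a time, or a total that brings in every escalation dose and schedule.

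The factor that varies across that total is the one the protocol expects to matter. Protocol 6.1.3.2 takes a Grade 3 or 4 event as more likely to come from adding TMZ than from pamiparib alone. Exposure shows the same problem: SAP 6.4.1 needs different duration formulas for daily, 7-day and 14-day TMZ, and cumulative TMZ dose in milligrams has little meaning when those schedules share a column.

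At stake is whether the report carries a planned, regimen-specific safety summary or leaves the reader to assemble one.

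**Working it through.** **1. Planned columns against the denominator of interest.**

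| Planned column | Source | Contains all RP2D patients? | Contains only RP2D patients? |
|---|---|---|---|
| Each escalation dose level | SAP 6, 6.4 | No | Only if that level is the RP2D and schedule |
| All escalation | SAP 6 | No | No |
| Each expansion cohort | SAP 6, 6.4; protocol 11.2 | No | Yes, if all started the Appendix 1 regimen |
| Both phases | SAP 6.4 | Yes | No |

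No row answers yes to both questions. The nearest exception is protocol 11.3.1, which tabulates AE-driven dose changes by dose level. It does not cover AE incidence, and SAP 6.4.1 does not repeat the grouping.

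**2. Composition of the total.** Protocol 11.4 plans 50 escalation and 200 expansion patients: 50 + 200 = 250, as stated. Six cohorts of 20-25 give 6 x 20 = 120 to 6 x 25 = 150 if no cohort is enlarged. The escalation share is:
- 200 in expansion: 50/250 = 20%
- 150 in expansion: 50/200 = 25%
- 120 in expansion: 50/170 = 29%

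These are upper limits for off-regimen escalation patients. The synopsis permits interim dose levels, so some escalation patients may have received the RP2D and schedule.

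**3. What the total estimates.** With E expansion patients at rate p and 50 escalation patients at rate q, the total estimates (50q + Ep)/(50 + E). It differs from p by the escalation share times (q - p), which is zero only if q = p. The documents give neither rate. The illustration below assumes p = 30% and treats all 50 escalation patients as off-regimen:

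| Assumed q | E = 120 | E = 150 | E = 200 |
|---|---|---|---|
| 50% | 35.9% | 35.0% | 34.0% |
| 15% | 25.6% | 26.3% | 27.0% |

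The shift can go either way. The planned escalation levels lie both below 60 mg (20 and 40 mg) and above it (80 and 120 mg).

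**4. Precision.** The exact two-sided 90% limits are the 5% point of Beta(x, n - x + 1) and the 95% point of Beta(x + 1, n - x). This method reproduces all ten rows of the plan's response-rate table: 8/20 gives 21.7-60.6% (stated 22-61%) and 10/25 gives 23.6-58.3% (stated 24-58%). Applied to an AE observed in 30% of patients:

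| Patients | 90% CI | Width (points) |
|---|---|---|
| 6/20, one cohort | 14.0-50.8% | 36.8 |
| 36/120, six cohorts of 20 | 23.1-37.6% | 14.5 |
| 45/150, six cohorts of 25 | 23.9-36.8% | 12.9 |
| 60/200, full planned expansion | 24.7-35.8% | 11.1 |

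The SAP does not specifically plan intervals for AE rates, so these figures only measure how much a pooled column would say.

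**5. What can be rebuilt.** Cohorts do not overlap, and SAP 6.4.3 counts each patient once within a system organ class and preferred term. Adding numerators and denominators across cohort columns, plus any escalation level at the RP2D, therefore gives the pooled incidence exactly. The same does not hold for the medians and quartiles that SAP 6.2.2 prescribes for continuous exposure measures. They cannot be combined from cohort columns and would have to be recomputed from patient-level data.

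**The case against.** The other side has several good points.

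- **Nothing is lost.** AE counts can be added by hand, and SAP 6.4.3 lists all AEs. This stands. A reader might infer that uncommon serious toxicity could go unseen because each cohort is small. The documents do not support that: the number of patients observed does not depend on column layout, and every event appears in a listing and, if treatment-emergent, in the total.
- **The total has a purpose.** The primary safety objective covers pulsed and continuous TMZ, which an all-phase column serves. This stands, so there is no case for removing or demoting it.
- **Separate reporting is deliberate.** The cohorts differ in tumour type and prior therapy, are to be evaluated separately (SAP Section 5), and protocol and SAP agree. This stands as a reason to keep the cohort columns, and there is no contradiction between the documents. It is not a reason to omit the pool, since the SAP already pools these cohorts with a more varied group.
- **Expansion may not stay on one regimen.** Protocol 4.3 allows up to 20 patients at a lower dose level, and protocol 4.2.1 allows a change of pamiparib schedule during or after escalation. This stands, and is why the new column should be defined by starting regimen and not by phase.

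Two other stronger readings also fail. One is that the SAP pools only across both phases; Section 6 also permits an all-escalation pool. The other is that the total overstates toxicity at the RP2D; the direction is unknown.

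**Conclusion.** The point holds as a gap in table planning and is best classed as a free improvement. No planned safety column has all patients on the recommended dose and schedule as its denominator. The one pool that includes them is up to 20% escalation patients at full planned enrolment, or 25-29% if expansion enrols 150-120. It estimates the RP2D rate only if escalation and RP2D rates are equal.

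The cost is the absence of a ready, precise estimate for the chosen regimen and of exposure medians and quartiles for that group. On the exact 90% interval for a 30% rate, going from one cohort of 20 to a pool of 120 narrows the range from about 14-51% to 23-38%.

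This rests on reading Appendix 1 as one TMZ regimen for all six cohorts and on planned, not actual, enrolment. The shares are upper limits for off-regimen patients, and the rates used to illustrate mixing are assumed.

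**What to change.** In SAP 6.4, add an All RP2D column to the exposure, TEAE, SAE, Grade 3 or above and laboratory-shift tables. Define it as all patients in the Safety Analysis Set whose starting regimen was the RP2D and schedule, in either phase, and state that later dose changes do not move a patient out of it. Show separately any expansion patients who started on another regimen under protocol 4.2.1 or 4.3. Keep the cohort columns. Keep the all-phase total, with a footnote that it mixes TMZ doses and schedules.

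The cost is one column in tables already planned and a flag for starting regimen derived from the dosing records. No new data are needed.
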